10.2. Appendix 2: Clinical Laboratory Tests

The following laboratory tests will be performed at times defined in the **SOA** section of this protocol. Additional laboratory results may be reported on these samples as a result of the method of analysis or the type of analyzer used by the clinical laboratory, or as derived from calculated values. These additional tests would not require additional collection of blood. Unscheduled clinical laboratory measurements may be obtained at any time during the study to assess any perceived safety issues.

Table 7. Protocol-Required Safety Laboratory Assessments

Hematology	Chemistry	Urinalysis	Other
Hemoglobin	BUN	pH	Lipid panel:
Hematocrit	Creatinine	Glucose (qual)	
 • Total cholesterol
RBC count	eGFR	Protein (qual)	
 • Direct LDL-C
MCV	Plasma glucose	Blood (qual)	
 • HDL-C
MCH	Calcium	Ketones	
 • Triglycerides
MCHC	Sodium	Nitrites	TSH
Platelet count	Potassium	Leukocyte esterase	Free T4
WBC count	Chloride	Urobilinogen	Calcitonin
Total neutrophils	AST	Urine bilirubin	Amylase
(Abs)	ALT	Microscopy ^a	Lipase
Eosinophils (Abs)	Total bilirubin	Urine pregnancy test	Serum total bile acids
Monocytes (Abs)	GGT		PT/INR/aPTT
Basophils (Abs)	Alkaline phosphatase		Serum pregnancy test (β -hCG)
Lymphocytes (Abs)	Uric acid		
	Albumin		
	Total protein		At screening and/or Day-2 only:
			
 • FSH^b • Urine drug screening^c • Hepatitis B surface antigen • Hepatitis B core antibody • Hepatitis C antibody • Human immunodeficiency virus • Syphilis
	Additional Tests (Needed for Hy's Law)		
	AST, ALT (repeat) Total bilirubin (repeat) Albumin (repeat) Alkaline phosphatase (repeat) Direct bilirubin Indirect bilirubin Creatine kinase GGT (repeat) PT/INR (repeat) Total bile acids Acetaminophen drug and/or protein adduct levels		

a. Only if urine dipstick is positive for blood, protein, nitrites, or leukocyte esterase.
 b. For confirmation of postmenopausal status only.
 c. The minimum requirement for drug screening includes cocaine, tetrahydrocannabinol, opiates/opioids, benzodiazepines, and amphetamines (others are site and study specific).

Investigators must document their review of each laboratory safety report.

After randomization, the investigator site and other blinded personnel will be blinded to plasma glucose obtained after the first dose of study intervention measured by the central laboratory, unless the FPG meets the criterion for hypo- or hyper-glycemia as listed in [Section 8.2.5.2](#) and [Section 8.2.5.3](#).

10.3. Appendix 3: Adverse Events: Definitions and Procedures for Recording, Evaluating, Follow-up, and Reporting

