2.2.2.1. Clinical Safety

Clinical data from the completed C3421001, C3421002, and C3421003 studies are provided in the IB for PF-06882961.

The results of C3421002, which is the only completed multiple dosing study in patients with T2DM to date, are summarized as below.

In study C3421002, PF-06882961 doses ranging from 10 mg BID to 120 mg BID were generally safe and well tolerated. A total of 98 participants with T2DM on a background of metformin were randomized to receive PF-06882961 or matching placebo in a 3:1 randomization ratio, and 92 participants completed the study. Six (6) participants discontinued from the study, of which 2 discontinuations were due to treatment-related TEAEs, and 4 withdrew during the treatment or follow-up period for non-treatment related reasons.

A total of 319 TEAEs were reported, of which the majority of the AEs (294 [92%]) were mild in intensity, 23 (7%) were moderate, and 2 (1%) were severe in intensity. The most frequently reported TEAEs were nausea (49.0%), dyspepsia (32.7%), vomiting (26.5%), diarrhea (24.5%), headache (23.5%), and constipation (20.4%). One (1) participant experienced a TEAE of hypoglycemia. This AE was non-fasting, mild in severity and of limited duration.

No deaths occurred in the C3421002 study. Two (2) participants experienced 2 severe TEAEs during the study, 1 of which occurred in the dosing period and was considered treatment related, the other occurred during the follow-up period and was not considered treatment related. The latter participant experienced 2 non-treatment-related SAEs, 1 of which occurred in the follow-up period and was a TEAE of severe intensity, and the other occurred outside of the study reporting period.

While there were isolated values for laboratory tests, vital signs and ECG intervals outside of the reference ranges, no clear adverse trends were apparent in these parameters. As has been reported for marketed GLP-1R agonists,^{10,11} increases in heart rate have been observed, with mean increases ranging from 5 to 15 bpm across doses administered to date, and most heart rate values were within the normal range.

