2.2.2.2. Clinical Pharmacokinetics

The clinical PK of PF-06882961 in healthy adult participants has been evaluated in three completed studies: C3421001, C3421002, and C3421003. The results of these completed studies are summarized in the PF-06882961 IB.

The PK properties of PF-06882961 have been evaluated in adult participants with T2DM as part of the completed C3421002 study. In this study, the first 6 cohorts received PF-06882961 or placebo dosed BID. Four of the 6 cohorts were titrated for various amounts of time over the 28 days, with a target maximum dose ranging between 10 and 120 mg BID across the 6 cohorts. Approximately dose proportional increases in C_{max} and AUC_{24} were observed between the doses of 10 mg BID and 120 mg BID, with C_{max} ranging from 38.38 to 685.2 ng/mL and AUC_{24} ranging from 455.9 to 8368 ng•h/mL. Percent coefficients of variance (%CV) ranged from 32 to 94 and 41 to 87 for C_{max} and AUC_{24} respectively on Day 28. Consistent with data from the completed studies, PF-06882961 was observed to have a $t_{1/2}$ of approximately 4.681 to 8.090 hours. T_{max} ranged from 3 to 6 hours after the AM dose over the dose ranges administered.

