8.2.5.1. Home Glucose Monitoring

- To aide in management of their T2DM, all participants will be provided home glucose monitoring supplies including a glucometer, instructions on the use of the glucometer and accompanying supplies.
- Home glucose monitoring logs will be provided to participants for completion at home and brought to each visit to the site along with the glucometers. Investigators must review the home glucose monitoring logs completed by the participants and the readings stored in the glucometer device at all time points listed in the [SOA](#).
- Participants must perform home glucose monitoring at least 3 times weekly following at least an 8-(preferably 10-) hour fast (except water). However, the investigator may recommend daily home glucose monitoring if needed.
- Less frequent glucose monitoring will NOT be considered a protocol deviation unless the participant fails to monitor his/her glucose for 3 or more consecutive days.
- If the participant experiences symptoms of hypoglycemia, home glucose monitoring should be performed, and these symptoms, along with the glucometer measurement, should be captured on the home glucose monitoring log.
- If the participant uses his/her own glucometer, and not one provided by the Sponsor, a protocol deviation will NOT be recorded provided the investigator is still able to monitor the participant's daily glucose values according to the criteria stated above.

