8.2.5.2.1. Definition and Severity of Categorization of Hypoglycemic Adverse Event (HAE)

Based on review of the participant completed home glucose monitoring log at each time point specified in the **SOA**, as well as results reported by the central laboratory, the investigator must assess the glucose values as well as any symptoms documented.

HAE is defined as **one** of the following: ¹⁵

1. **Asymptomatic hypoglycemia:** An event *not* accompanied by typical symptoms of HAE but a glucose value of <70 mg/dL (3.9 mmol/L) using either glucometer (FSBG) or sponsor-identified central laboratory (plasma glucose);
2. **Documented symptomatic hypoglycemia:** An event during which typical symptoms of HAE are accompanied *with* a glucose value of <70 mg/dL (3.9 mmol/L) using glucometer (or sponsor-identified central laboratory) **and** the clinical picture includes prompt resolution with food intake, subcutaneous glucagon, or glucose administration;
3. **Probable symptomatic hypoglycemia:** An event during which symptoms of HAE are *not* accompanied by a glucose determination but was presumably caused by a glucose concentration of <70 mg/dL (3.9 mmol/L), **and** the clinical picture includes prompt resolution with food intake, subcutaneous glucagon, or glucose administration.

Each episode of HAE must be categorized with respect to severity. In order to characterize the event as severe, **all three (3) criteria** below must be met:

1. The participant was unable to treat himself/herself. Neurologic impairment, and not the age of the participant, is the explanation for why the participant could not treat himself/herself and required the assistance of another person.
2. The participant exhibited at least one of the following neurological symptoms:
 - Memory loss;
 - Confusion;
 - Uncontrolled behavior;
 - Irrational behavior;
 - Unusual difficulty in awakening;

- Suspected seizure;
- Seizure;
- Loss of consciousness.

3. Either:

- If blood glucose was measured and was ≤ 54 mg/dL (2.7 mmol/L) using glucometer (or central laboratory); or
- If blood glucose was not measured, the clinical manifestations were reversed by oral carbohydrates, subcutaneous glucagon, or glucose administration.

Events that do not meet all the criteria above for severe HAE are characterized as mild or moderate in severity.

Any episode of HAE must be captured on the HAE CRF.

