8.2.5.3. Management of Hyperglycemia

Hyperglycemia is defined as the following:

- Fasting glucose ≥ 270 mg/dL (15.0 mmol/L) using glucometer (or central laboratory).

After randomization, participants noted to have a fasting glucose value (during home glucose monitoring) meeting the above definition of hyperglycemia must be instructed to repeat the measurement the next day (following at least an 8 [preferably 10] hour fast, except water). If the second measurement also meets the above definition, participants must be asked to contact the site and return to the site a day later (following at least an 8 [preferably 10] hour fast, except water) and have blood collected for FPG (and shipped to the central laboratory for analysis).

The investigator should determine if the participant collected the samples after an adequate fasting period; and if the participant is following recommended dietary guidelines. Proper dietary and collected procedures should be reinforced with the participant.

If the results from the central laboratory confirm the readings using glucometer, the participant should be discontinued, and the investigator will recommend further appropriate glycemic treatment according to the local healthcare standards and national guidelines.

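### The glucose blinding rule releases only fasting values to the site, but the hypoglycemia definition also counts non-fasting central-laboratory values, so asymptomatic events may be missing from the CRF-based summary

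*Protocol*

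**What the plan says.** **Blinding rule.** Under Protocol Section 10.2 (Appendix 2), the site and other blinded staff do not see plasma glucose obtained after the first dose and "measured by the central laboratory, unless the FPG meets the criterion for hypo- or hyper-glycemia as listed in" Sections 8.2.5.2 and 8.2.5.3. The trigger is the fasting plasma glucose (FPG).

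**HAE definition.** Protocol Section 8.2.5.2.1 defines asymptomatic hypoglycemia as an event without typical symptoms "but a glucose value of <70 mg/dL (3.9 mmol/L) using either glucometer (FSBG) or sponsor-identified central laboratory (plasma glucose". There is no fasting condition. The same section has the investigator assess glucose values from the home log and from central-laboratory reports. Section 8.2.5.2 requires each episode to be entered on the CRF.

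**Hyperglycemia definition.** Protocol Section 8.2.5.3 does set a fasting condition: "Fasting glucose ≥ 270 mg/dL (15.0 mmol/L) using glucometer (or central laboratory".

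**Analysis.** SAP Section 3.1.1.1, placed under the primary endpoint, assigns the asymptomatic category when the CRF shows no symptoms, glucose measured, a result below 70 mg/dL, and the event not classed as severe. SAP Section 6.1.1.1 and Protocol Section 9.4.5.1 summarize HAEs by category. SAP Section 6.1.4 lists and summarizes laboratory data separately.

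**The concern.** The release rule and the definition use different criteria. The FPG trigger fits hyperglycemia, which is defined on fasting glucose, but it is narrower than the hypoglycemia definition it points to. A participant can have a measured value that is an HAE by the protocol's own words while the rule keeps that value from the investigator who has to record it.

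Two things are at stake. The first is the asymptomatic row of the HAE summary, which is part of the primary safety evaluation: it can be incomplete for a reason unrelated to the drug. The second is that the site cannot act on a value it has not been shown. The study is descriptive, with about 9 participants per arm, so even one or two missing events would change how a row of that table reads.

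**Working it through.** The plan states no figure on this point, so the check is a comparison of the texts, followed by a bound on how many values could be involved.

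**Step 1. Apply both rules to the same central-laboratory result, obtained after the first dose in a participant without symptoms.**

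| Result | Meets the event definition? | Released to the site under Appendix 2? |
|---|---|---|
| Fasting, 60 mg/dL | Yes (8.2.5.2.1) | Yes |
| Non-fasting, 60 mg/dL | Yes (8.2.5.2.1) | No |
| Fasting, 270 mg/dL or more | Yes (8.2.5.3) | Yes |
| Non-fasting, 270 mg/dL or more | No (8.2.5.3 is fasting only) | No |

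The rules agree in three rows. They conflict in the second, and only for hypoglycemia.

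**Step 2. Follow the second row into the analysis.** The site does not see 60 mg/dL, so it has no result to enter on the hypoglycemia CRF page. The SAP algorithm needs a CRF result below 70 mg/dL, so the event is not assigned to the asymptomatic category. The value remains in the laboratory dataset, but neither document maps laboratory glucose to HAE categories.

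**Step 3. Ask where such a value could come from.**

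- *Scheduled chemistry:* Table 1 places activities at 0H, before the morning meal and dose, unless stated otherwise. Table 2 places Day 56 chemistry at 0H. Section 5.3.1 requires an 8-hour fast before the first sample at screening, on inpatient days and at outpatient and follow-up visits. Visible scheduled chemistry is therefore fasting and does not fall in the second row.
- *Unscheduled chemistry:* Section 8.2 allows extra laboratory tests whenever a safety question arises, and Table 7 includes plasma glucose in the chemistry panel. Nothing requires such a sample to be fasting. This route is fully visible, but its frequency is unknown.
- *Day 56 mixed-meal test:* Section 5.3.1.2 describes post-dose blood draws through 4 hours. The analytes are redacted, so whether glucose is assayed cannot be seen.

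**Step 4. Bound the scheduled values that could be withheld on Day 56.** This assumes all 36 participants complete every draw.

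- No redacted Table 2 row is plasma glucose: 0 values.
- Glucose is assayed through 4 hours (0.25, 0.5, 1, 1.5, 2, 3 and 4 h, so 7 post-dose times): 7 × 36 = 252 values.
- Glucose is assayed through 12 hours (adding 6, 8, 10 and 12 h, so 11 times): 11 × 36 = 396 values.

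These are counts of results, not of low results. The documents give no basis for estimating how many would be below 70 mg/dL.

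**The case against.** The strongest reply is that the conflict may have little practical effect. Visible scheduled chemistry is fasting and would be released. The only plausible scheduled non-fasting source is redacted, and its procedure section, also not visible, could contain its own release rule. Section 8.2.5.2.1 speaks of results the laboratory reports, which could be taken to mean only those the site receives. Safety laboratory data are reviewed during the study (Protocol Section 9.4.2), and specified sponsor staff are unblinded (Section 6.3.2). The protocol also expects little hypoglycemia with this drug class when insulin and sulfonylureas are prohibited.

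Most of this stands as a limit on extent. It does not remove the conflict: the definition and the duty to record every episode carry no fasting condition, and no visible text tells the sponsor to pass a non-fasting low value to the site or to classify it as an HAE.

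A reader might be tempted by three stronger readings, which the documents do not support.

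- *Fasting-only routine checks cause events to go unrecorded.* Home checks are indeed fasting ("Participants must perform home glucose monitoring at least 3 times weekly following at least an 8-(preferably 10-) hour fast (except water"), as are the scheduled on-site and inpatient glucometer checks. But the asymptomatic category needs a measured value. A post-dose low that nobody measures is not an HAE under the definition. That is a sampling choice, not an effect of blinding.
- *Checks far from peak concentration must miss the drug's effect.* Time to peak "ranged from 3 to 6 hours after the AM dose over the dose ranges administered", but concentration relative to peak does not measure hypoglycemia risk or missed events, and the protocol describes the drug's insulin effect as glucose-dependent.
- *The one earlier event proves the gap.* Of that event in the completed 28-day study the protocol says: "This AE was non-fasting, mild in severity and of limited duration". It does not say that the event was asymptomatic, near peak concentration or found by laboratory glucose. A symptomatic event would prompt a glucometer check here.

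**Conclusion.** The point holds as a conflict between the Appendix 2 release rule and the Section 8.2.5.2.1 definition. As written, a non-fasting central-laboratory glucose below 70 mg/dL after the first dose meets the HAE definition but is withheld from the site, and it may be absent from the CRF-based asymptomatic summary. It is not lost altogether, because it stays in the laboratory data.

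The size is unknown and may be small. Scheduled exposure ranges from 0 to 252 or 396 withheld results of any level, all on Day 56, depending on redacted rows; unscheduled chemistry adds an unknown number. The conclusion assumes that FPG in Appendix 2 is meant literally and that no redacted text supplies a separate rule. The conflict itself rests on visible text alone.

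**What to change.** Reconcile the two passages in one or both of these ways.

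1. **Protocol Appendix 2.** Extend the release rule to any post-dose central-laboratory plasma glucose, fasting or not, that meets the Section 8.2.5.2.1 value. Keep the FPG trigger for hyperglycemia, where it matches the definition. This takes one sentence in an amendment. The downside is the rare disclosure of an isolated low value to the site, which the protocol already accepts for FPG.
2. **SAP Section 3.1.1.1.** Identify asymptomatic HAEs from central-laboratory glucose below 70 mg/dL as well as from the CRF, showing the source and counting an episode found in both only once. This costs some programming and discloses nothing to the site. Used alone, it leaves the site unaware of the value, and absence of symptoms would have to be inferred from the lack of a CRF entry. The SAP should state that convention.

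If redacted text already covers release of mixed-meal glucose, a cross-reference from Appendix 2 would settle that source and leave only unscheduled samples to be addressed. No additional sampling is needed to resolve the conflict.

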10.3.1. Definition of AE

AE Definition

• An AE is any untoward medical occurrence in a patient or clinical study participant, temporally associated with the use of study intervention, whether or not considered related to the study intervention.• NOTE: An AE can therefore be any unfavorable and unintended sign (including an abnormal laboratory finding), symptom, or disease (new or exacerbated) temporally associated with the use of study intervention.

Events Meeting the AE Definition

• Any abnormal laboratory test results (hematology, clinical chemistry, or urinalysis) or other safety assessments (eg, ECG, radiological scans, vital sign measurements), including those that worsen from baseline, considered clinically significant in the medical and scientific judgment of the investigator. Any abnormal laboratory test results that meet any of the conditions below must be recorded as an AE:
• Is associated with accompanying symptoms;• Requires additional diagnostic testing or medical/surgical intervention;• Leads to a change in study dosing (outside of any protocol-specified dose adjustments) or discontinuation from the study, significant additional concomitant drug treatment, or other therapy.• Exacerbation of a chronic or intermittent preexisting condition including either an increase in frequency and/or intensity of the condition.• New conditions detected or diagnosed after study intervention administration even though it may have been present before the start of the study.• Signs, symptoms, or the clinical sequelae of a suspected drug-drug interaction.• Signs, symptoms, or the clinical sequelae of a suspected overdose of either study intervention or a concomitant medication. Overdose per se will not be reported as an AE/SAE unless it is an intentional overdose taken with possible suicidal/self-harming intent. Such overdoses should be reported regardless of sequelae.

Events NOT Meeting the AE Definition

- Any clinically significant abnormal laboratory findings or other abnormal safety assessments which are associated with the underlying disease, unless judged by the investigator to be more severe than expected for the participant's condition.
- The disease/disorder being studied or expected progression, signs, or symptoms of the disease/disorder being studied, unless more severe than expected for the participant's condition.
- Medical or surgical procedure (eg, endoscopy, appendectomy): the condition that leads to the procedure is the AE.
- Situations in which an untoward medical occurrence did not occur (social and/or convenience admission to a hospital).
- Anticipated day-to-day fluctuations of preexisting disease(s) or condition(s) present or detected at the start of the study that do not worsen.

10.3.2. Definition of SAE

If an event is not an AE per definition above, then it cannot be an SAE even if serious conditions are met (eg, hospitalization for signs/symptoms of the disease under study, death due to progression of disease).

An SAE is defined as any untoward medical occurrence that, at any dose:

a. Results in death

b. Is life-threatening

The term “life-threatening” in the definition of “serious” refers to an event in which the participant was at risk of death at the time of the event. It does not refer to an event that hypothetically might have caused death if it were more severe.

c. Requires inpatient hospitalization or prolongation of existing hospitalization

In general, hospitalization signifies that the participant has been detained (usually involving at least an overnight stay) at the hospital or emergency ward for observation and/or treatment that would not have been appropriate in the physician's office or outpatient setting. Complications that occur during hospitalization are AEs. If a complication prolongs hospitalization or fulfills any other serious criteria, the event is serious. When in doubt as to whether “hospitalization” occurred or was necessary, the AE should be considered serious.

Hospitalization for elective treatment of a preexisting condition that did not worsen from baseline is not considered an AE.

d. Results in persistent disability/incapacity

- The term disability means a substantial disruption of a person's ability to conduct normal life functions.
- This definition is not intended to include experiences of relatively minor medical significance such as uncomplicated headache, nausea, vomiting, diarrhea, influenza, and accidental trauma (eg, sprained ankle) which may interfere with or prevent everyday life functions but do not constitute a substantial disruption.

e. Is a congenital anomaly/birth defect

f. Other situations:

- Medical or scientific judgment should be exercised in deciding whether SAE reporting is appropriate in other situations such as important medical events that may not be immediately life-threatening or result in death or hospitalization but may jeopardize the participant or may require medical or surgical intervention to prevent one of the other outcomes listed in the above definition. These events should usually be considered serious.
- Examples of such events include invasive or malignant cancers, intensive treatment in an emergency room or at home for allergic bronchospasm, blood dyscrasias or convulsions that do not result in hospitalization, or development of drug dependency or drug abuse.
- Suspected transmission via a Pfizer product of an infectious agent, pathogenic or non-pathogenic, is considered serious. The event may be suspected from clinical symptoms or laboratory findings indicating an infection in a patient exposed to a Pfizer product. The terms "suspected transmission" and "transmission" are considered synonymous. These cases are considered unexpected and handled as serious expedited cases by pharmacovigilance personnel. Such cases are also considered for reporting as product defects, if appropriate.

